## **10.2. Plan and Timeline of Proposed Analyses**

In general the study is designed to have 80% power or greater for detecting hazard ratios of 2 or greater for exposures 10% or greater, based on the expectation of being able to enroll 7,013 subjects from the general population and 788 relatives in five years, with 15 years of post-accrual follow-up. The actual study experience may be different and it is prudent to provisionally plan for interim analyses. In doing so, we consider the following caveats: 1) Laboratory determinations made for interim analysis of stored samples need to be identical to the laboratory methods of the same determinations to be made at the end of the study if the data are to be aggregated, and 2) Some longitudinal testing of stored samples is prudent to ensure sample integrity and quality.

#### **10.2.1. Protocol Monitoring**

Protocol compliance in terms of screening, recruitment, and collection of protocol defined biological samples, questionnaires, and diaries will be monitored on a

monthly basis. This report will summarize the accrual to the study (including maternal registrations), the demographic distribution of the subjects on study, the HLA distribution, and other baseline variables available. Accrual rates will be contrasted with expected or planned rates for Steering Committee review. Monthly reports will also be prepared from the data accumulating on laboratory monitoring quality assurance programs as specified by the Laboratory Monitoring Committee. Calculations of protocol compliance rates are based upon the tests/samples/forms due as a function of the age of enrolled subjects.

Also, we plan to monitor monthly parameters that provide estimates of psychological impact of study participation and parental satisfaction with study participation.

#### **10.2.2. Exposure Monitoring**

Since most exposures are measured from the analysis of biological samples, little will be available in the interim to assess exposure rates. Yet, we believe it is prudent to try to obtain some measures to ensure that sample collection procedures are adequate. To this end, we will target samples in which we may have more than enough volume. For example, current sample collection procedures suggest that volume will not be a problem for stool specimens and we may periodically sample the cohort to conduct interim analyses of viral exposures. In that we project collecting in excess of 26,000 stools samples in the first year, we would plan to sample the 1-year cohort to conduct these preliminary analyses. We no not expect to have surplus blood volumes to conduct interim analyses since all blood volume study requirements were based upon the minimal amounts needed for the study analyses.

Where exposure rates can be estimated from diaries, questionnaires, psychological assessments (e.g., anxiety, depression, behavior changes, stress) and food frequency instruments will be tabulated cumulatively and as a function of subjects' age. These tabulations will also be made monthly. Risk factors with unanticipated exposure rates will be discussed and adjustments to power calculations made as appropriate.

Retention of study participants is a high priority and we will provide continuous assessment of study dropouts. These analyses will include baseline demographics and environmental exposures for comparison with subjects continuing the study cohort.

#### 10.2.3. Outcome analysis

After five and ten years of accrual, interim analyses of the prospective portion of the study will be performed and reported to the participating investigators. These analyses will address the relationships of the triggers being studied to the development of T1DM using the same Cox Proportional Hazards Regressions

planned for final analyses. Tables 12 and 13 present power calculations for these interim analyses for the general population. Note that a 4% conversion rate at 15 years for those unexposed implies conversion rates of 1.4% and 2.7% at 5 and 10 years respectively, assuming exponential conversion.

As the study progresses, we will have a more accurate picture of accrual and follow-up rates and estimates of some exposure rates based upon the diaries and questionnaires. As well, we will be able to observe cases of autoimmunity and T1DM and base our planned analyses on these rather than projections. For some environmental triggers, assessed from the entire prospective cohort, we will be able to schedule interim analyses. Our first priority will be to confirm, or not, previous reports of risk factors that have been reported in the literature. For example, the study will have an early picture of diet. Literature reports of risk factors with hazard ratios of 3 or greater can be tested in interim analyses with reasonable power. Examples of these might be:

- Food supplementation with gluten containing foods before age 3 months (reported hazard ratio 4.0, 95% CI 1.4-11.5).
- Children initially exposed to cereals between ages 0 and 3 months (reported hazard ratio 4.3, 95% CI 2.0-13.8)
- Vitamin D supplementation (2000 IU daily) compared to those who regularly received less (relative risk 0.22, 95% CI 0.05-0.89)

And from the maternal study:

• CVB5 in maternal sera collected in the first trimester of pregnancy (OR 10, 95% CI 1.4-43.4)

For most of these, the literature report includes a minimum of 4-6 years of followup. For other hypotheses that can be tested in the interim, the duration of followup will be the rate-limiting factor as well as many of the other studies in the literature report calculated risk in children up to 15 years of age. TEDDY investigators will propose additional hypotheses to be tested and, prior to conducting interim analyses, each will be evaluated with respect to the detectable hazard ratio at a minimum of 80% power. We recognize that this leads to increased chances of finding associations as a result of increasing studywide type

1 error, but as a hypothesis forming epidemiological study we will balance this against the calculated hazard ratios and exercise caution in our interpretations.

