## 4. Objectives

The primary objective of this study is to identify environmental factors that predispose to or protect from beta-cell autoimmunity and T1DM.

The secondary objectives include:

[figure not shown]
- 1. Identification of potential differences in the environmental determinants of T1DM across diverse populations and ethnic groups.
- 2. Identification of potential differences in the environmental determinants of T1DM between children with and without first-degree T1DM relatives.
- 3. Establishment of a central repository for data and biologic samples for subsequent hypothesis based research.
- 4. Exploration of psychosocial corollaries of the ascertainment of risk status for autoimmunity and T1DM in newborns.
- 5. Exploration of gene-environmental interactions.
- 6. Better understanding of the natural history of the disease.

[figure not shown]

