Ov	er 5 years	General Population	on FDF	ł			
Enroll		7,013	788				
Cases - autoantibodies by age 6		281 (4%)	105 (13.	3%)			
Cases - T1DM by age 15		281 (4%)	105 (13.	3%)			

Based on submissions by the participating institutions, we expect to be able to enroll 7,013 subjects from the general population and 788 relatives in five years. Those from the general population and the relatives are expected to have about 4% and 13.3% autoimmune conversion at 6 years respectively. Tables 6-13 below give the power for a Log Rank Test at a two-sided 0.01 significance level for the general population subjects, the relatives, and the pooled sample accrued over 5 years with 15 years of post-accrual follow-up for dichotomous pre-birth triggers of frequencies 1%, 5%, 10%, and 20% and hazard ratios of 1.5 and 2.0 and losses to follow-up at rates of 0%, 2%, 5%, and 10% per year. These calculations are based on the method of Lakatos (Lakatos, 1998) using a computer program described by Cantor (Cantor, 2003).

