5100.180.7510100.370.96	1	10	0.04	0.14
10 10 0.37 0.96				

Table 9: Power for Prospective Study – General Population – Autoantibodies End Point, Alpha = .01, N = 7013, 5 Years Accrual, Follow-Up to age 15, 4% Conversion among Unexposed at 6 Years

$\begin{array}{cccccccccccccccccccccccccccccccccccc$	
5 0 0.66 0.99	
10 0 0.93 0.99	
10 0.00	
20 0 0.99 0.99	
1 2 0.10 0.47	
5 2 0.57 0.99	
10 2 0.88 0.99	
20 2 0.99 0.99	
1 5 0.07 0.36	
5 5 0.45 0.99	
10 5 0.78 0.99	
20 5 0.96 0.99	
1 10 0.05 0.25	
5 10 0.31 0.93	
10 10 0.60 0.99	
20 10 0.87 0.99	

Table 10: Power for Prospective Study –Relatives – Autoantibodies End Point,
Alpha = $.01$ , N = 788, 5 Years Accrual, Follow-Up to age 15,
13.3% Conversion among Unexposed at 6 Years

Exposed %	LTFU %/year	Power ( HR = 1.5)	Power ( HR = 2.0)
1	0	0.03	0.12
5	0	0.16	0.67
10	0	0.34	0.94
20	0	0.61	0.99
1	2	0.03	0.10
5	$\frac{2}{2}$	0.03	0.10
10	2	0.29	0.89
20	2	0.52	0.99
1	5	0.03	0.08
5	5	0.11	0.48
10	5	0.22	0.80
20	5	0.42	0.97
1	10	0.02	0.06
5	10	0.08	0.35
10	10	0.15	0.65
20	10	0.29	0.89

Table 11: Power for Prospective Study – Pooled Sample – Autoantibodies End Point Alpha = .01, N = 7801, 5 Years Accrual, Follow-Up to age 15, 5.5% Conversion among Unexposed at 6 Years

Exposed %	LTFU %/year	Power ( HR = 1.5)	Power (HR = 2.0)
1	0	0.15	0.68
5	0	0.78	0.99
10	0	0.98	0.99
20	0	0.99	0.99
1	2	0.12	0.56
5	2	0.67	0.99
10	2	0.94	0.99
20	2	0.99	0.99
1	5	0.12	0.56
5	5	0.67	0.99
10	5	0.94	0.99
20	5	0.99	0.99
1	10	0.08	0.40
5	10	0.49	0.99
10	10	0.82	0.99
20	10	0.98	0.99

Table 12: Interim Analysis Power for Prospective Study- General Population –Diabetes End Point, Alpha = .01, N = 7013, 5 Years Accrual, Follow-Up to age 5, 1.4% Conversion among Unexposed at 5 Years

Exposed %	LTFU %/year	Power ( HR = 2.0)	Power (HR = 3.0)	Power $(Hr = 5.0)$
1	0	0.08	0.42	0.98
5	0	0.50	0.99	0.99
10	0	0.81	0.99	0.99
20	0	0.97	0.99	0.99
1	2	0.08	0.39	0.97
5	2	0.46	0.99	0.99
10	2	0.78	0.99	0.99
20	2	0.95	0.99	0.99
1	5	0.07	0.34	0.95
5	5	0.41	0.98	0.99
10	5	0.72	0.99	0.99
20	5	0.93	0.99	0.99
1	10	0.06	0.28	0.91
5	10	0.34	0.95	0.99
10	10	0.63	0.99	0.99
20	10	0.87	0.99	0.99

Table 13: Interim Analysis Power for Prospective Study- General Population –Diabetes End Point, Alpha = .01, N = 7013, 5 Years Accrual, Follow-Up to age 10, 2.7% Conversion among Unexposed at 10 Years

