Exposed %	LTFU %/year	Power ( HR = 2.0)	Power (HR = 3.0)	Power ( HR = 5.0)
1	0	0.14	0.66	0.99
5	0	0.75	0.99	0.99
10	0	0.96	0.99	0.99
20	0	0.99	0.99	0.99
1	2	0.12	0.59	0.99
5	2	0.69	0.99	0.99
10	2	0.94	0.99	0.99
20	2	0.99	0.99	0.99
1	5	0.10	0.50	0.99
5	5	0.59	0.99	0.99
10	5	0.89	0.99	0.99
20	5	0.99	0.99	0.99
1	10	0.08	0.38	0.97
5	10	0.46	0.99	0.99
10	10	0.77	0.99	0.99
20	10	0.95	0.99	0.99

The above tables demonstrate that a trigger will have to be associated with a hazard ratio of about 2.0 in order for us to have reasonable power. In that case, we will have adequate power for exposure rates of at least 5% if we have little (not exceeding 2% per year) loss to follow-up. If we have more losses to follow-up, we will need to have at least a 10% exposure rate for a trigger with a hazard ratio of 2.0.

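### Power is tabulated only for exposures that raise risk, yet a protective example (vitamin D, RR 0.22) is listed among effects said to have reasonable interim power

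*Protocol*

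**What the plan says.** Section 4 sets the primary objective as to "identify environmental factors that predispose to or protect from beta-cell autoimmunity and T1DM", so protection is in scope.

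Section 10.3 states that Tables 6-13 "give the power for a Log Rank Test at a two-sided 0.01 significance level" and that "These calculations are based on the method of Lakatos". Tables 6-11 use hazard ratios of 1.5 and 2.0, Tables 12-13 use 2, 3 and 5, and Tables 14-16 use odds ratios of 1.5 and 2.0. None is below 1. The paragraph after Table 13 concludes that "a trigger will have to be associated with a hazard ratio of about 2.0 in order for us to have reasonable power". Section 10.2 makes the matching general claim: at least 80% power for a hazard ratio of 2 at 10% exposure.

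On the interim analyses, Section 10.2.3 says "Literature reports of risk factors with hazard ratios of 3 or greater can be tested in interim analyses with reasonable power". Its list of possible examples includes "Vitamin D supplementation (2000 IU daily) compared to those who regularly received less (relative risk 0.22, 95% CI 0.05-0.89". The only interim power given is in Table 12 ("N = 7013, 5 Years Accrual, Follow-Up to age 5, 1.4% Conversion among Unexposed at 5 Years") and Table 13 ("Follow-Up to age 10, 2.7% Conversion among Unexposed at 10 Years").

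**The concern.** An RR of 0.22 is as far from 1 on the log scale as an HR of 1/0.22 = 4.55, which invites the reader to look it up between the HR 3 and HR 5 columns. That works only if the test has similar power in both directions. It does not when the exposed group is small: a harmful exposure adds events to that group, while a protective one removes events from a group that has few to lose.

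Section 10.2.3 makes it the first priority to confirm or not confirm published risk factors. If the protected group is a small minority, a null interim result for a truly protective factor could be read as a failure to confirm when the test had little chance of succeeding. The same gap affects the general power claims in Sections 10.2 and 10.3 at the final analysis.

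**Working it through.** **Inputs.** N = 7013, two-sided alpha 0.01 (critical value 2.576), log-rank test, exponential conversion, no loss to follow-up. Unexposed conversion is 1.4% at 5 years and 2.7% at 10 years (Tables 12-13), which Section 10.2.3 derives from 4% at 15 years. The frequency of the vitamin D exposure is not in the protocol; 5%, 10% and 20% are assumed because the tables use them.

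**Formula.** With d1 the expected exposed events, d all events and π the exposed share of those at risk, summed over time:

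z = Σ(d1 − dπ) / √Σ dπ(1 − π), power = Φ(|z| − 2.576).

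**Reproducing the plan.** Five years' uniform accrual plus 5 further years (5+5), HR 2, 10% exposed: d1 = 29.02, null expectation 15.95, variance 14.37. So z = 13.07/3.79 = 3.45 and power = Φ(0.87) = 0.81, as Table 12 prints. The same model gives 0.495 for HR 2 at 5% (printed 0.50) and 0.415 for HR 3 at 1% (printed 0.42). The 5+10 model gives 0.963 and 0.747 against 0.96 and 0.75 in Table 13. Following every child to exactly age 5, as Table 12's heading suggests, gives 0.599 where 0.81 is printed. Both readings are therefore shown.

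**RR 0.22, first interim.** On 5+5 at 10% exposed: d1 = 3.26, null expectation 13.63, variance 12.26. So z = −10.38/3.50 = −2.96 and power = Φ(0.39) = 0.65. Using the unrounded rate implied by 4% at 15 years, 1 − 0.96^(1/3) = 1.35%, it is 0.63. The approximations below use that unrounded rate. The simulations (2,000-3,000 replicates) use the rounded rates.

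| Look and follow-up | Method | 5% exposed | 10% | 20% |
|---|---|---|---|---|
| First interim, 5+5 | approximation | 0.31 | 0.63 | 0.93 |
| | simulation | 0.19 | 0.79 | 0.99 |
| First interim, exactly to age 5 | approximation | 0.19 | 0.42 | 0.77 |
| | simulation | 0.00 | 0.41 | 0.91 |
| Table 12 as printed, HR 3 and HR 5 | | 0.99 | 0.99 | 0.99 |
| Second interim, exactly to age 10 | approximation | 0.43 | 0.78 | 0.98 |
| | simulation | 0.41 | 0.93 | 1.00 |
| Second interim, 5+10 | approximation | 0.54 | 0.88 | 1.00 |
| | simulation | 0.64 | 0.98 | 1.00 |

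**Why the simulation is so low at 5%.** To age 5, about 7013 × 0.95 × 0.014 = 93.3 unexposed events are expected. With no exposed event at all, |z| = √(93.3 × 0.05/0.95) = 2.22, short of 2.576. On 5+5 there are about 139.4 unexposed events. No exposed event gives √(139.4 × 0.05/0.95) = 2.71, while one gives (140.4 × 0.05 − 1)/√(140.4 × 0.05 × 0.95) = 2.33. Significance then needs roughly zero exposed events when 1.63 are expected: e^−1.63 = 0.20, in line with the simulated 0.19.

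**Loss to follow-up.** At 5% per year on 5+5, simulated power falls to 0.06 at 5% exposed and 0.61 at 10%.

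**Final analysis, HR 0.5, 10% exposed.** The first figure follows each child to age 15; the second uses 5+15 years, which reproduces Table 6 for HR 2.0 (0.89 at 5% exposed, 0.99 at 10%).

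- General population, T1DM: 0.51-0.59, against 0.99 printed for HR 2.0.
- Pooled, T1DM, at Table 8's 5.5%: 0.74-0.81.
- General population, autoantibodies, at Table 9's 4% by age 6: 0.93-0.96.

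**The case against.** The strongest reply is about coding. Section 5 (hypothesis 1c) and Section 8.14.6.1 frame the vitamin D question as low intake raising risk. With low intake as the index group the ratio is 4.55 and fits the sentence. If that group is 5-10% of children and 1.4% is the rate among the supplemented, power to age 5 is about 0.99 or more. If the 1.4% belongs to the low-intake group, simulated power is 0.62 at 5% and 0.84 at 10%. This stands as far as it goes: the example is not an error under every coding. But the bullet itself makes supplementation the index group and states neither coding nor prevalence.

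The second reply is that prevalence is unknown, that Section 10.2.2 promises to adjust power for observed exposure rates, and that Section 10.2.3 promises an 80%-power check. The first part stands: at 50% exposed the approximation gives 0.99 to age 5. The promises do not close the gap. The first says nothing about direction of effect, and the second concerns additional hypotheses, not the listed examples.

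Three stronger readings are tempting and not supported:

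- A reader might infer that interim power for vitamin D lies between nothing and about 0.42. That covers only the first interim at 5-10% exposure, on a follow-up reading that does not reproduce Table 12's figures.
- Taking the first look literally at five calendar years, with children aged 0-5, gives simulated power of about zero at 5-10% exposed. Neither Table 12's heading nor its figures match that timing.
- A reader might infer that halving the risk always needs about 20% exposure. The autoantibody result at 10% exposure (0.93-0.96) refutes this as a general rule.

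**Conclusion.** Wrong as written. The tables cover only ratios above 1, and the interim statement extends them to a protective effect that they do not describe. At an assumed 5% exposure, first-interim power for RR 0.22 is at most about 0.32 by any method used here. At 10% it is 0.41-0.79, depending on follow-up and method, where a reader of Table 12 would expect 0.99. At 20% it is 0.77 or better without loss. The second interim is clearly better: adequate or close to it at 10% (0.78-0.98), still weak at 5% (0.41-0.64).

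The final-analysis result needs no assumption about vitamin D. For general-population T1DM at 10% exposure, halving the risk has a little over half the power printed for doubling it. The gap is much smaller in the pooled sample and small for autoantibodies.

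These figures assume exponential conversion and, except where noted, no loss to follow-up. The documents do not support saying that a true vitamin D effect would probably go unconfirmed, because neither the exposure share nor the coding is stated.

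**What to change.** 1. In Section 10.2.3, take the vitamin D example out of the statement on large hazard ratios, or state which group is the index group and give the example's own interim power over a range of exposure rates.
2. Add protective columns (for instance HR 0.67, 0.5 and 0.33) to Tables 6-13 from the same program. Where few exposed events are expected, check the entries by simulation.
3. In Section 10.2 and in the paragraph after Table 13, say that the power claims are for exposures that raise risk. Give protective power by endpoint and population, not as a single exposure threshold.

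The cost is one more run of an existing program and a few sentences, with no change to design or data collection. The downside is that the stated power for protective factors becomes less favourable.

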#### **10.3. Sample size and power determination**

Subjects will be recruited over a five-year period and followed until they reach the age of 15 years old. Thus all subjects will have 15 years of follow-up.

#### Table 5

	Screening/y remaining 3 accru	years of	Eligible/year for remaining 3 years of accrual		Enroll/year for remaining 3 years of accrual			rual		
Center	General Population	FDR	Eligibility Rate GP	General Population	Eligibility Rate FDR	FDR	Enrollment Rate GP	General Population	Enrollment Rate FDR	FDR
Colorado	16,316	176	5.1%	832	23.5%	41	42%	350	64%	26
Finland	11,204	132	5.6%	627	35.1%	46	44%	276	60%	28
Georgia/Florida	14,272	172	3.5%	500	16.4%	28	33%	165	50%	14
Germany	7,296	356	3.9%	285	19.5%	69	30%	85	80%	56
Sweden	8,956	220	7.6%	681	18.3%	40	65%	442	65%	26
Washington State	23,628	204	3.9%	921	26.7%	54	37%	341	75%	41
TOTAL:	81,672	1,260		3,846		278		1659		191

	Actual total screened by site for first 2		Projected total screened b	y site for remaining	Total screened by site for 5 years of accrual	
	years of accrual		3 years of a	ccrual		
Center	General Population	FDR	General Population	FDR	General Population	FDR
Colorado	17,896	296	48,948	528	66,844	824
Finland	22,827	271	33,612	396	56,439	667
Georgia/Florida	25,204	226	42,816	516	68,020	742
Germany	6,695	526	21,888	1,068	28,583	1,594
Sweden	17,991	358	26,868	660	44,859	1,018
Washington State	20,363	139	70,884	612	91,247	751
TOTAL:	110,976	1,816	245,016	3,780	355,992	5,596

Actual total eligible by s accru		•	Projected total eligible 3 years of		Total eligible by site accrual	Total eligible by site for 5 years of accrual	
Center	General Population	FDR	General Population	FDR	General Population	FDR	
Colorado	811	66	2,496	123	3,307	189	
Finland	1,254	94	1,881	138	3,135	232	
Georgia/Florida	824	34	1,500	84	2,324	118	
Germany	244	99	855	207	1,099	306	
Sweden	1,282	61	2,043	120	3,325	181	
Washington State	635	28	2,763	162	3,398	190	
TOTAL:	5,050	382	11,538	834	16,588	1,216	
	Actual total enrolled by	site for first 2 years of	Projected total enrolled by site for remaining 3 years of accrual		Total enrolled by site for 5 years of accrual		
	accri	ual					
Center	General Population	FDR	General Population	FDR	General Population	FDR	
Colorado	262	35	1,050	78	1,312	113	
Finland	556	43	828	84	1,384	127	
Georgia/Florida	204	15	495	42	699	57	
Germany	72	69	255	167	327	236	
Sweden	796	40	1,326	78	2,122	118	
Washington State	146	14	1,023	123	1,169	137	
TOTAL:	2,036	216	4,977	572	7,013	788	
Ov	er 5 years	General Population	on FDF	ł			
Enroll		7,013	788				
Cases - autoantibodies by age 6		281 (4%)	105 (13.	3%)			
Cases - T1DM by age 15		281 (4%)	105 (13.	3%)			

Based on submissions by the participating institutions, we expect to be able to enroll 7,013 subjects from the general population and 788 relatives in five years. Those from the general population and the relatives are expected to have about 4% and 13.3% autoimmune conversion at 6 years respectively. Tables 6-13 below give the power for a Log Rank Test at a two-sided 0.01 significance level for the general population subjects, the relatives, and the pooled sample accrued over 5 years with 15 years of post-accrual follow-up for dichotomous pre-birth triggers of frequencies 1%, 5%, 10%, and 20% and hazard ratios of 1.5 and 2.0 and losses to follow-up at rates of 0%, 2%, 5%, and 10% per year. These calculations are based on the method of Lakatos (Lakatos, 1998) using a computer program described by Cantor (Cantor, 2003).

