## Table 6: Power for Prospective Study- General Population –Diabetes End Point, Alpha = .01, N = 7013, 5 Years Accrual, Follow-Up to age 15, 4% Conversion among Unexposed at 15 Years

Exposed %	LTFU %/year	Power ( HR = 1.5)	Power ( HR = 2.0 )
1	0	0.05	0.21
5	0	0.26	0.89
10	0	0.52	0.99
20	0	0.81	0.99
1	2	0.04	0.17
5	2	0.21	0.82
10	2	0.44	0.98
20	2	0.72	0.99
1	5	0.03	0.13
5	5	0.16	0.71
10	5	0.34	0.95
20	5	0.59	0.99
1	10	0.03	0.09
10	10	0.23	0.83
20	10	0.42	0.98
5 10	10 10	0.11 0.23	0.52 0.83

Table 7: Power for Prospective Study- Relatives – Diabetes End Point Alpha = .01, N = 788, 5 Years Accrual, Follow-Up to age 15, 13.3% Conversion among Unexposed at 15 Years

Exposed %	LTFU %/year	Power (HR = 1.5)	Power ( HR = 2.0)
1	0	0.02	0.06
5	0	0.07	0.33
10	0	0.14	0.62
20	0	0.27	0.87
1	2	0.02	0.05
5	2	0.06	0.27
10	2	0.12	0.53
20	2	0.22	0.80
1	5	0.02	0.04
5	5	0.05	0.21
10	5	0.09	0.42
20	5	0.17	0.68
1	10	0.02	0.03
5			0.03
	10	0.04	
10	10	0.06	0.29
20	10	0.11	0.51

Table 8: Power for Prospective Study- Pooled Sample – Diabetes End Point,
Alpha = $.01$ , N = 7801, 5 Years Accrual, Follow-Up to age 15,
5.5% Conversion among Unexposed at 15 Years

$\begin{array}{c ccccccccccccccccccccccccccccccccccc$	Exposed %	LTFU %/year	Power ( HR = 1.5)	Power ( HR = 2.0 )
$ \begin{array}{c ccccccccccccccccccccccccccccccccccc$				
$\begin{array}{c ccccccccccccccccccccccccccccccccccc$	1	0	0.07	0.35
$\begin{array}{c ccccccccccccccccccccccccccccccccccc$	5	0	0.43	0.98
$\begin{array}{c ccccccccccccccccccccccccccccccccccc$	10	0	0.75	0.99
$ \begin{array}{cccccccccccccccccccccccccccccccccccc$	20	0	0.95	0.99
$\begin{array}{c ccccccccccccccccccccccccccccccccccc$	1	2	0.06	0.29
$\begin{array}{c ccccccccccccccccccccccccccccccccccc$	5	2	0.35	0.96
$\begin{array}{c ccccccccccccccccccccccccccccccccccc$	10	2	0.66	0.99
$ \begin{array}{cccccccccccccccccccccccccccccccccccc$	20	2	0.91	0.99
$ \begin{array}{cccccccccccccccccccccccccccccccccccc$				
$\begin{array}{cccccccccccccccccccccccccccccccccccc$		5	0.05	0.22
20         5         0.82         0.99           1         10         0.04         0.14           5         10         0.18         0.75           10         10         0.37         0.96	5	5	0.27	0.90
1         10         0.04         0.14           5         10         0.18         0.75           10         10         0.37         0.96	10		0.54	0.99
5100.180.7510100.370.96	20	5	0.82	0.99

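### Tables 6 and 8 credit children with 15 to 20 years of follow-up although follow-up ends at age 15, so T1DM power is overstated by up to about 8 points; the general-population case called adequate is 0.76, not 0.82

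*Protocol*

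**What the plan says.** Two accounts of follow-up stand side by side in the protocol.

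- **To age 15.** Section 10.3 opens by recruiting over five years and following each child to age 15: "Thus all subjects will have 15 years of follow-up". The Timetable in Section 1 staggers close-out at age 15 over 2019-2024, and Section 13.4 tells families the same end point. The headings of Tables 6 and 8 also say so: "N = 7013, 5 Years Accrual, Follow-Up to age 15" and "N = 7801, 5 Years Accrual, Follow-Up to age 15".
- **Fifteen years after accrual closes.** Section 10.2 describes the design as five years of enrolment "with 15 years of post-accrual follow-up". Section 10.3 says the power tables are for "the pooled sample accrued over 5 years with 15 years of post-accrual follow-up for dichotomous pre-birth triggers". On this account the first children enrolled are followed to age 20.

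The test is a "Log Rank Test at a two-sided 0.01 significance level", with power by the Lakatos method. After Table 13, Section 10.3 concludes that at a hazard ratio of about 2.0 the study has "adequate power for exposure rates of at least 5% if we have little (not exceeding 2% per year) loss to follow-up". The Table 6 cell for that case is 0.82.

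**The concern.** Both accounts cannot be true, and the choice changes the number of events. If the printed powers rest on the longer follow-up, they include T1DM between ages 15 and 20. The study does not observe that period, and Section 10.3 itself projects T1DM cases only to age 15. What is at stake is the reliability of the T1DM power tables. Section 10.9 refers readers to the tables to judge how departures in exposure, loss or accrual affect detectable risk. One design statement, the adequacy of 5% exposure with up to 2% annual loss, rests for general-population T1DM on a cell close to 80%.

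**Working it through.** **Inputs (Protocol).** Two-sided alpha 0.01, log-rank, Lakatos method (Section 10.3). N = 7,013 with 4% conversion in the unexposed at 15 years (Table 6). N = 7,801 with 5.5% (Table 8). Exponential conversion (Section 10.2.3). Exposure 1, 5, 10 and 20%; hazard ratio (HR) 1.5 and 2.0; loss 0, 2, 5 and 10% per year.

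**Formulas.** For Table 6, λ₀ = −ln(0.96)/15 = 0.00272 per year and λ₁ = HR × λ₀. Let p be the exposed fraction, η the loss rate and A(s) the fraction not yet administratively censored at time s. Then

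- n₀(s) = (1−p)·exp[−(λ₀+η)s]·A(s) and n₁(s) = p·exp[−(λ₁+η)s]·A(s);
- d(s) = (n₀λ₀ + n₁λ₁)ds and φ = n₁/n₀;
- E = √N · Σ d[φ·HR/(1+φ·HR) − φ/(1+φ)] / √(Σ d·φ/(1+φ)²);
- power = Φ(E − 2.576).

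Two follow-up patterns are compared:

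- *5+15*: A = 1 to year 15, then (20−s)/5 to year 20.
- *Fixed 15*: A = 1 to year 15, then 0.

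**Events by hand (Table 6, 5% exposed, HR 2.0, no loss).**

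- Fixed 15: 7,013 × [0.95 × 0.04 + 0.05 × (1 − 0.96²)] = 7,013 × 0.04192 = 294.
- 5+15, using the mean follow-up of 17.5 years: 7,013 × [0.95 × (1 − 0.96^(17.5/15)) + 0.05 × (1 − 0.96^(35/15))] = 7,013 × 0.04873 = 342.

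The ratio is 342/294 = 1.16. At 2% annual loss the expected events are 288 against 254.

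**Reproducing the printed powers (loss as an annual rate).**

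| Cell | Printed | 5+15 | Fixed 15 |
|---|---|---|---|
| Table 6, 5% exposed, HR 2.0, 0% loss | 0.89 | 0.890 | 0.830 |
| Table 6, 5%, HR 2.0, 2% loss | 0.82 | 0.821 | 0.761 |
| Table 6, 5%, HR 2.0, 5% loss | 0.71 | 0.703 | 0.652 |
| Table 6, 10%, HR 2.0, 10% loss | 0.83 | 0.831 | 0.805 |
| Table 6, 20%, HR 1.5, 0% loss | 0.81 | 0.803 | 0.728 |
| Table 8, 5%, HR 1.5, 0% loss | 0.43 | 0.424 | 0.359 |
| Table 8, 10%, HR 1.5, 0% loss | 0.75 | 0.748 | 0.669 |
| Table 8, 5%, HR 2.0, 2% loss | 0.96 | 0.958 | 0.930 |

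On 5+15 all 32 cells of Table 6 agree within 0.01, and all 30 legible cells of Table 8 within 0.02. On a fixed 15 years only 13 to 14 cells of each table agree within 0.02.

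**Could a different N explain it?** The interim tables at the same N = 7,013 show the same pattern. Table 12 (5% exposed, HR 2.0, no loss) prints 0.50; five years' accrual plus five gives 0.495, a fixed five years 0.317. The matching cell of Table 13 prints 0.75; 5+10 gives 0.747, a fixed ten years 0.630.

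**The claim in Section 10.2 (HR 2, exposure 10% or more, at least 80%).** With a fixed 15 years, 10% exposure and loss of 0, 2, 5 and 10%, Table 6 becomes 0.985, 0.967, 0.922 and 0.805. Table 8 becomes 0.999, 0.998, 0.991 and 0.952.

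**The case against.** The strongest reply is that little turns on this. Section 1 reports 8,677 children followed against 7,801 projected. If about 90% are general population, as planned (7,013/7,801 = 89.9%), that is about 7,800 children and the disputed cell returns to 0.81. About 7,600 suffice for 0.80, or 7,600/8,677 = 87.6% of the cohort. Section 10.3 sets no threshold for adequacy and names no population. At 5% exposure and 2% loss with follow-up to 15, pooled T1DM has 0.93 and the general-population autoantibody end point 0.99. No test, sample or decision rule changes. All of this stands and limits the consequence, but it does not make the printed tables correct.

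Three stronger inferences are tempting and are not supported.

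- *That the headline claim in Section 10.2 fails.* The nearest case is general-population T1DM at 10% exposure and 10% loss. A value of 0.79 arises there only if loss is converted as −ln(1−d). That convention gives 0.816 for a cell printed as 0.83 and matches only 26 of 32 Table 6 cells within 0.01. Loss as a rate matches all 32 and gives 0.805.
- *That the pooled cohort also drops below 80% in the case called adequate.* It does not; its cell is 0.93.
- *That Table 7 (relatives) contradicts its heading,* "N = 788, 5 Years Accrual, Follow-Up to age 15, 13.3% Conversion among Unexposed at 15 Years". With exactly those inputs and a fixed 15 years, the HR 2.0 cells without loss are 0.32, 0.61 and 0.86, against 0.33, 0.62 and 0.87 printed. A smaller N of about 707 on the 5+15 basis fits slightly more closely, but that figure appears nowhere in the protocol and is only a back-fit. Table 7 shows no overstated power.

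**Conclusion.** The point holds for Tables 6 and 8. Their headings say follow-up to age 15, but their numbers come from five years' accrual plus 15 years, and power is overstated by up to about 8 points. At the planned N, general-population T1DM at HR 2.0 and 5% exposure has power 0.83, 0.76 and 0.65 at 0, 2 and 5% loss, not 0.89, 0.82 and 0.71. The case Section 10.3 calls adequate therefore falls about four points below the 80% used as a benchmark in Sections 10.1, 10.2 and 10.2.3. This rests on the protocol's own inputs: exponential conversion, two-sided 0.01 and projected enrolment. The 0.76 does not depend on the loss convention (0.760 or 0.761). The recovery to about 0.81 rests on the assumed 90% general-population share of those followed. The tables are wrong as written and should be corrected, but the error does not show that the study as a whole is underpowered.

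**What to change.** 1. Recompute Tables 6 and 8 with every child administratively censored at age 15. Show both the planned N and the enrolment achieved, split into general population and relatives.
2. In Sections 10.2 and 10.3, replace the phrase on post-accrual follow-up by follow-up to age 15, in line with the opening of Section 10.3.
3. Qualify the closing paragraph of Section 10.3. For general-population T1DM at the planned N, 5% exposure with 2% annual loss gives 0.76; the pooled cohort keeps 0.93. The power claim in Section 10.2 needs no change beyond the follow-up phrase.
4. When the tables are re-issued, state the follow-up basis of Table 7 and the loss convention used.

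The cost is one recalculation and a few lines of text. Some stated powers become less favourable. No procedure, sample or visit changes.
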